1 STUDY OBJECTIVES

To conduct a pilot trial to determine the feasibility, safety, and potential efficacy of targeting MAP within the limits of cerebral autoregulation during hip, knee, or lung surgery compared with usual care.

2 BACKGROUND AND RATIONALE

Surgery for hip fracture in particular can be devastating for older adults, with complications that include delirium,¹ inability to walk unaided,² and 1-year mortality >20%.³ Other types of major surgery in older adults, including other major orthopedic surgery and lung surgery can also have a high incidence of delirium that ranges up to 20%. During many types of surgery, extreme variations in blood pressure are common in older adults due to age-associated vascular and autonomic dysfunction.⁴ However, there is no standard of care as to what constitutes adequate blood pressure in individual patients during surgery to avoid cerebral ischemia, with over 80 empiric definitions of hypotension in the literature.⁵

Our group has championed a more precise method for defining optimal blood pressure in individual patients than the current practice of empiric targets. Through the process of cerebral autoregulation, the brain is exquisitely regulated to maintain a constant cerebral blood flow across a wide range of mean arterial pressures (MAP).⁶ However, when MAP declines below the lower limit of autoregulation (LLA) or rises above the upper limit of autoregulation (ULA), compensatory mechanisms fail and cerebral hypo- or hyperperfusion can occur. We have developed validated methods to identify the LLA and ULA in real-time in individual patients, and using these methods during cardiac surgery, we have found several key results. First, the MAPs at the LLA and ULA varied tremendously among individuals, implying that “one size fits all” blood pressure targets are inadequate.⁷ Second, the extent that MAP varied above and below the limits of cerebral autoregulation was associated with postoperative delirium⁸ and kidney injury,⁹ implying that hypo- or hyperperfusion may lead to organ dysfunction.

Finally, and most importantly, an intervention to maintain MAP during cardiac surgery within a patient’s limits of cerebral autoregulation reduced delirium compared with usual care (in pilot data from a trial conducted by my mentor).

However, the results of this trial in cardiac surgery may not apply in other surgeries due to differences in patients and surgical insult. It is also unclear if MAP can be effectively targeted in the other surgery populations. To address this gap in knowledge, we plan to determine the feasibility, safety, and potential efficacy of targeting MAP within the limits of cerebral autoregulation during a more generalizable group of surgeries, including hip or knee surgery (fracture or periprosthetic revision) or lung surgery compared with usual standard of care.

3 STUDY DESIGN

3.1 Study Design Overview

We will conduct a randomized, double-masked controlled trial. We will enroll 25 patients with usable data. Randomization will be 2:1 in intervention vs. standard arm with stratification by orthopedic vs. lung surgery in permuted blocks of 3 or 6 (i.e. each surgical strata will have the opportunity for 17 intervention patients and 8 control patients to be enrolled).

Patients randomized to the intervention arm will have their MAP targeted within the limits of cerebral autoregulation during surgery. Patients randomized to the standard arm will receive observational monitoring.

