5.3 Randomization

Randomization will be 2:1 in intervention vs. standard arm with stratification by orthopedic vs. lung surgery in permuted blocks of 3 or 6 (i.e. each surgical strata will have the opportunity for 17 intervention patients and 8 control patients to be enrolled). A patient will be considered to be randomized when they enter the operating room and the anesthesiologist is handed a sealed opaque envelope indicating the study allocation.

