5.4 Description of Intervention and Control

The critical difference will be blood pressure targets during surgery. Cerebral autoregulation monitoring will begin prior to anesthesia induction, with the LLA and/or ULA anticipated to be available within 30 minutes. The methods are described in the subsequent section “Intraoperative Monitoring of Cerebral Autoregulation.” These values will be used to establish blood pressure targets.

In the intervention group, at 30 minutes after the start of monitoring, [name] will visualize the autoregulation curves. Upon confirmation of an adequate curve, a blood pressure target will be provided to the anesthesiologist. [name] will visualize the autoregulation curves every 30-60 minutes to update the blood pressure target as necessary. The lower limit of autoregulation will not be <55 mm Hg. or >90 mm Hg.

In the intervention arm, the anesthesia provider will target MAP>LLA with the following strategy: reduce anesthetic agent while maintaining adequate anesthetic depth as clinically determined, IV fluid administration, and vasopressor infusion (likely dopamine or levophed, but at the discretion of the anesthesiologist). MAP<ULA will be targeted with the following strategy: vasodilator infusion (likely nicardipine or nitroglycerine, but at the discretion of the anesthesiologist) or other clinical approaches as decided by the anesthesiologist. If the treating anesthesiologist or surgeon feels that the blood pressure target is too high or too low for clinical reasons, then they will request a different target, and this request will take priority. In the control arm, the anesthesia provider will use usual care guidelines, which is generally systolic blood pressure >90 mm Hg.

FEAT Study Protocol

Patients will be allowed to be enrolled in other studies. Adherence will be assessed as part of the feasibility outcomes.

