6.2 Reporting Procedures

All adverse events are evaluated by [name] and two other Johns Hopkins faculty with respect to intensity, frequency, relationship to study, and outcome.

The protocol for the FEAT trial for reporting AE is the following:

- All AE are recorded on an AE form.
 - a. The AE may be identified from a list of pre-defined complications or from informal review of the electronic medical record by research staff.
 - b. Serious AE will be further recorded on a separate form.
 - c. A panel of three faculty at Johns Hopkins (including [name]) will adjudicate expectedness and relatedness of each AE.
- Serious AE (SAE)
 - a. If **unexpected**, SAE will be reported to the NIA, IRB, and the independent safety officer within 48 hours.
 - b. If **expected**, then SAE will be reported using the SAE form within 14 days of discovery.
 - c. An SAE will be considered expected if it is listed in the DSMP and/or the adjudication committee considers it expected (with consideration that events with <5% incidence should be considered unexpected).
- Non-serious AE that are unexpected, possibly related, and may place participants at greater harm than originally recognized will be reported to the IRB, NIH, and the independent safety officer within 14 days.
- All other adverse events will be maintained in the study database and reported to the IRB during continuing review and to the safety officer every **6 months**.

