7. STATISTICAL CONSIDERATIONS

7.1. Outcomes:

Primary outcome variables

Feasibility outcomes will be recruitment >60%, enrollment of at least 3 patients per month, available lower limit of autoregulation target in >65% of all patients, at least 1 delirium assessment in >95%, and at least 1 cognitive and functional assessment in >90%.

Safety outcomes will be increased operative bleeding and significant organ ischemia (myocardial infarction, as judged by treating physicians).

Secondary clinical outcome variables

Extent of mean arterial pressure outside the limits of cerebral autoregulation (after the establishment of the MAP target) will be assessed based on intraoperative monitoring data.

FEAT Study Protocol

Delirium will be assessed in the hospital using the 3D-CAM (CAM-ICU for intubated patients).

Cognitive and functional outcomes will be assessed by telephone at postoperative days 60 and 180, and in-person or by telephone at 1-year follow-up.

- a. Cognitive outcomes are: Short Blessed Test score, Oral Trail Making Test Score, AD8 score
- b. Functional outcomes are: inability to walk ≥ 10 feet without human assistance, WHO-DAS 2.0 score, Instrumental Activities of Daily Living, and institutionalization

7.2. Analytic Plan:

We will examine whether targeting MAP based on the limits of cerebral autoregulation during surgery is feasible and safe, and we will explore whether it can reduce delirium, improve cognition, and improve function. The primary goal is to assess feasibility and safety of the intervention. We will monitor success in implementing each aspect of the protocol, and performance and safety metrics will be compared against pre-specified criteria as defined in the primary outcome section.

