8.3 Quality Assurance

Because our group has been conducting an observational study using similar assessments and monitoring over the past several years, study coordinators are experienced in the administration of the patient assessments, autoregulation monitoring, and data abstraction. and will train research staff. The study coordinator will train any additional research staff, including co-evaluating patients, oversight of patient interactions after independence, and periodic audit of data collection. The study team will meet weekly to discuss all aspects of the study.

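### The trial is called double-masked but never says who is masked, and myocardial infarction, a primary safety outcome, is left to treating physicians, some of whom can know the arm

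*Combined protocol and SAP*

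**What the plan says.** - **Label.** Section 3.1 announces a "randomized, double-masked controlled trial". No other section mentions masking, names a masked role or gives a procedure.
- **Allocation.** Under section 5.3, "the anesthesiologist is handed a sealed opaque envelope indicating the study allocation" as the patient enters the operating room.
- **Target.** Under section 5.4, once an adequate curve is confirmed in the intervention arm, "a blood pressure target will be provided to the anesthesiologist". The same section provides for the case "If the treating anesthesiologist or surgeon feels that the blood pressure target is too high or too low for clinical reasons", so the surgeon may know the target as well.
- **Safety outcome.** Section 7.1 lists safety under the primary outcome variables. It names increased operative bleeding, with no assessor stated, and organ ischemia, given as "myocardial infarction, as judged by treating physicians".
- **Panel.** Section 6.2 has three faculty members evaluate adverse events for outcome, relationship to the study, intensity and frequency. It adds that the panel "will adjudicate expectedness and relatedness of each AE". Events reach the panel from a pre-defined list or from an informal record review by research staff.
- **Assessors.** Sections 5.2.5 and 7.1 specify the 3D-CAM (CAM-ICU if intubated) and the follow-up instruments, but not who administers them. Section 8.3 says that "study coordinators are experienced in the administration of the patient assessments, autoregulation monitoring, and data abstraction".

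**The concern.** Section 7.2 makes feasibility and safety the primary goal. Whether an MI has occurred can be a matter of judgement. A physician who knows that a patient was managed to an individual pressure target may look harder for ischemia, or be readier to explain it away, so the error can run in either direction. Following section 7.1 as written leaves this decision with clinicians who can know the arm, and no stated later step revisits it without that knowledge.

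The delirium comparison carries a weaker form of the same question. The 3D-CAM is rated by an interviewer, and section 7.2 intends the between-group differences as a benchmark for deciding on a further trial. If the results are reported as double-masked, readers will assume protections for both outcomes that the plan does not describe.

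**Working it through.** The point rests mainly on the text. The arithmetic only shows how much a single event weighs.

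**1. Who can know the arm**

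| Role | Source | What the plan supports |
|---|---|---|
| Patient | 3.1 | Masking implied by the label, not described |
| Anesthesiologist | 5.3, 5.4 | Knows the arm; receives the target in the intervention arm |
| Surgeon | 5.4 | May contest the target, so may know it |
| Physicians judging MI | 7.1 | Can include the two above, or later clinicians who never saw the envelope; nothing shields any of them |
| Faculty panel | 6.2 | Not described as masked; not stated to confirm events |
| Research staff finding events | 6.2 | Masking not stated |
| 3D-CAM and follow-up assessors | 5.2.5, 7.1, 8.3 | Identity and masking not stated |

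The MI row is the firm one, because there the plan does state a rule. The assessor row is silence.

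**2. Whether the panel closes the MI gap.** Its listed tasks are outcome, relationship, intensity, frequency and expectedness. All of them concern an event already recorded as such. Deciding whether an MI occurred is not on the list.

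**3. The plan's own precision figure.** Section 7.3 gives 16 percentage points for delirium with n = 25. It states no incidence, so I assume 20%, the upper figure that section 2 gives for major surgery other than hip fracture:

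1.96 × √(0.20 × 0.80 / 25) = 0.157, or 16 points.

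The figure reproduces. Assumed incidences of 10%, 30% and 50% give 11.8, 18.0 and 19.6 points. None of these depends on masking.

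**4. Weight of one event.** Sections 3.1 and 5.3 give 17 and 8 as the places available in each surgical stratum. I assume the same split overall, since 2:1 of 25 is 16.7 to 8.3.

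- Intervention: 1/17 = 5.9 points.
- Control: 1/8 = 12.5 points.

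Incomplete blocks could shift the split slightly. With 16:9 the weights are 1/16 = 6.3 and 1/9 = 11.1 points; with 18:7 they are 1/18 = 5.6 and 1/7 = 14.3 points.

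**5. What is not exposed.** The feasibility criteria in section 7.1 count recruitment, enrollment, available targets and completed assessments. None depends on how an assessor scores a patient.

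**The case against.** The strongest reply is that double-masked often means patient plus outcome assessor. Someone who titrates pressure to a target has to know the arm, so an unmasked anesthesiologist contradicts nothing. That stands. A reader might infer that the masking claim is false or has failed; the documents support only that the masked roles and procedures are not described.

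A reader might also infer from section 8.3 that the same coordinators run a patient's monitor and then score that patient's delirium. The text does not say so. It describes experience gained in an observational study and a training role, not assignments per patient in this trial. Standard-arm patients are monitored too (section 3.1), so running the monitor does not by itself reveal the arm, although being present when a target is given could.

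Three further replies have some force. Physicians who judge MI after surgery may not know the arm. The panel's remit is wider than expectedness and relatedness. Section 6.2 also refers to a DSMP and a list of pre-defined complications that are not part of the documents, so event definitions may exist there. None of these supplies a masked decision on whether an MI occurred.

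Finally, this is a pilot and efficacy is only explored. That limits the consequence for delirium, but not for safety, which the plan puts among its primary outcomes.

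**Conclusion.** The point holds in a limited form. The plan asserts double masking without saying who is masked or how, and its stated rule leaves a primary safety outcome to physicians some of whom can know the arm. The panel, as described, does not correct this. For delirium and follow-up assessments the finding is an omission to fill, not evidence that assessors were unmasked.

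One event is worth about 5.9 points in the intervention arm and 12.5 in the control arm, given an overall 17:8 split. It would be tempting to read these as the size of the bias. They are the weight of any single event in a trial this small, masked or not, and the documents give no basis for estimating bias.

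The change is worth making because the MI rule can be improved at small cost with a panel that already exists. It does not put the feasibility conclusions in doubt.

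**What to change.** 1. **Section 3.1.** Describe the trial as patient- and outcome-assessor-masked with the anesthesia team unmasked, and say how each masked role is kept masked.
2. **Sections 6.2 and 7.1.** Give the existing panel a two-step task. First, working from extracts with allocation and pressure targets removed and against written criteria, it decides whether each suspected MI or operative bleeding event occurred. Only then does it judge relatedness, with allocation available, because relatedness to the intervention is hard to judge without it. Any member who read that patient's autoregulation curves abstains from the first step. Names are removed from the public text, so I cannot tell whether such overlap exists. If one of three abstains, the plan should say how a disagreement between the other two is settled.
3. **Sections 5.2.5 and 8.3.** State that anyone in the operating room when a patient's target was given does not perform that patient's 3D-CAM or follow-up assessments where rostering allows, and record exceptions.

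The cost is protocol wording, redaction of a limited number of charts, a two-step review and less scheduling flexibility. Staffing numbers are not given, so doing this without new staff is an assumption. Enrollment already depends on staff being free to monitor in the operating room (section 5.2.1), so a rigid roster rule could press on the target of three patients a month. That is why item 3 allows recorded exceptions.

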3.2 Perioperative Care

FEAT Study Protocol

All anesthetic care will be according to usual practice, except the targeting of mean arterial pressure in the intervention group. This trial will not specify general or regional anesthesia, and this decision will be left up to the clinical team. Generally, this is as follows: for general anesthesia, induction with propofol (1-2mg/kg) or etomidate (0.1-0.3 mg/kg); maintenance with volatile anesthetic titrated to 0.5-1.0 MAC; and pain control with fentanyl (2-5 mcg/kg) or dilaudid (10-20 mcg/kg). An epidural may be used as appropriate. Depth of sedation may be titrated using a BIS monitor to 40-60. For patients who receive spinal anesthesia, the protocol may be: spinal anesthesia with isobaric bupivacaine, propofol (1-2 mcg/kg/min) for sedation, and fentanyl (1-3 mcg/kg) as needed for pain. Sedation may be titrated to a level consistent with arousability to voice. Surgical technique will be based on usual clinical practice for patients enrolled.

3.3 Intraoperative Monitoring of Cerebral Autoregulation

For monitoring of cerebral autoregulation, we will obtain digital signals from at least one or as many as three of the following monitors that are non-invasive and low-risk. First, the near infrared spectroscopy (NIRS) monitor measures regional oxygen saturation in the brain using two adhesive pads placed on the patient's forehead. The NIRS monitor will always be used. These monitors are FDA-approved and are standard of care during cardiac surgery at Johns Hopkins. Second, the Clearsight monitor is a non-invasive measure of real-time arterial blood pressure using a finger cuff. This device is FDA-approved and routinely used in operating rooms. If the patient has an arterial line, the arterial waveform will be extracted directly from the anesthesia monitor. Third, the Bispectral Index (BIS) is a non-invasive FDA-approved device also used in operating rooms to measure the depth of anesthesia using two adhesive pads that are placed on the patient's forehead.

The waveforms obtained from the NIRS, Clearsight or arterial line, and BIS monitors will be analyzed using dedicated software. In this paragraph, we describe how the data inputs from these three monitors are processed to calculate key measures of the adequacy of cerebral autoregulation and organ perfusion. NIRS measures regional cerebral oxygen saturation (rScO₂) and is weighted toward venous blood, thus indicating the adequacy of O₂ supply versus demand. Our group has demonstrated that rScO₂ provides a clinically acceptable surrogate of CBF for clinical autoregulation monitoring.^{11,15} Arterial pressure waveforms are obtained from the Clearsight monitor or arterial line. Both of these signals will be sampled with an analog-to-digital converter using ICM+ software (the University of Cambridge, Cambridge, UK) at 60 Hz. These signals will then be time-integrated as non-overlapping 10-second mean values, which is equivalent to applying a moving average filter with a 10-second time window and re-sampling at 0.1 Hz. This operation eliminates high frequency noise from the respiratory and pulse frequencies, according to the Nyquist theorem, allowing detection of oscillations and transients that occur below 0.05 Hz. A continuous, moving Pearson's correlation coefficient will be performed between the mean arterial pressure (MAP) and rScO₂, rendering the variable COx (cerebral oximetry index). Consecutive, paired, 10-second averaged values from 300-second duration will be used for each calculation, incorporating 30 data points for each index. This methodology has been previously validated. The MAP at the lower and upper limits of autoregulation will be indicated by the MAP at which COx transitions from approximately <0.3 to >0.3.

4. SELECTION AND ENROLLMENT OF PARTICIPANTS

4.1 Patients

Specific **inclusion criteria** are:

- Planned hip or knee surgery (either for fracture or periprosthetic revision), or lung surgery
- Age ≥ 60
- Ambulatory at baseline.

FEAT Study Protocol

- Expected duration of surgery > 90 minutes

Specific exclusion criteria

- Planned concurrent surgery
- Allergy to adhesive tape
- Short Blessed Test score >20
- Clinical diagnosis of dementia
- Opinion of either the anesthesiologist or surgeon that the patient is not appropriate.

Because of the age of these patients, it is anticipated that they will suffer from chronic diseases common in the elderly. However, each patient will be healthy enough to undergo the proposed operation, as judged by both the surgical and anesthesia services according to usual clinical practice.

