5. STUDY PROCEDURES

5.1. Schedule of Evaluations

Name	HOSPITALIZATION PHASE								FOLLOW-UP PHASE (± 30 days)		
	Screening	Baseline	Day of Surgery	Intraop monitoring	POD 1	POD 2	POD 3	Post Discharge	Day 60	Day 180	Day 365
Demography	✓										
Registration and Contact		✓									
Short Blessed Test		✓									
AD8 (patient or proxy)		✓									
Eligibility Confirmation		✓									
Baseline Exam (Pain scales, OTMT, WHO-DAS 2.0, IADL, BRS, 3D-CAM)		✓									
NIRS Monitoring			✓	✓							
Clearsight or arterial monitoring			✓	✓							
BIS monitoring			✓	✓							
Randomization and Intervention			✓	✓							
Surgery Data Collection									✓		
Postoperative Assessment (3D-CAM, Pain, Adverse Events)					✓	✓	✓				
Discharge Contact Info								✓			
Postoperative Events (Pain, Discharge contact)									✓		
Follow-up (Patient or Proxy) (60, 180, 365 days)									✓	✓	✓
AD8 (Patient or Proxy; 365 days)											✓
Adverse Events			✓		✓	✓	✓	✓	✓	✓	✓
End of Study											✓

¹WHODAS or WHODAS-Proxy to be used as appropriate.

FEAT Study Protocol

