5.2.3 Baseline Data

The following data will be collected onto case report forms (CRFs)

- Participant ID/Screening
- Registration and Contact Information
- Eligibility Confirmation
- Baseline Exam
- Baseline Pain Assessment
- 3D CAM
- Short Blessed Test
- Oral Trail Making Test
- AD8 (patient or proxy)
- WHODAS (or WHODAS Proxy)
- Instrumental Activities of Daily Living
- Brief Resilience Scale

FEAT Study Protocol

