We will then assess potential efficacy of the intervention to optimize blood pressure management, reduce delirium, improve SBT score, and improve functional status. The first analysis will be by intention-to-treat by randomization status with primary outcomes of extent of mean arterial pressure outside the limits of autoregulation after establishment of a target, frequency of delirium, change in Short Blessed Test score, and change in WHO-DAS score. We will calculate the mean or frequency of each outcome and between group differences, each with associated 95% confidence intervals. The former will provide estimates of variability in outcomes needed in power calculations for a definitive trial, and the latter will provide a benchmark by which pursuit of a further trial can be evaluated. We will then examine differences in characteristics between groups and in multivariable regression models adjusted for surgery type and age. Finally, we will examine secondary outcomes, including change in OTMT, conversion to dementia, and inability to walk 10-feet. Together, these analyses will inform selection and measurement of primary and secondary outcomes, as well as confounding variables, for a future trial powered for efficacy.

7.3. Sample Size:

Based on the experience of the investigative team, a sample size of 25 patients would allow determination of whether feasibility outcomes had been met and assessment of safety events. Such information would be critically important to support a future trial.

We also calculated a formal sample size to have adequate precision for estimating the primary outcome of delirium. We estimate that a sample size of n=25 would provide the precision to estimate the incidence of delirium to within 16 percentage points using a 95% CI.

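### The walking outcome has no matching baseline item, so patients who already need human help to walk can enter and be counted as postoperative failures

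*Combined protocol and SAP*

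**What the plan says.** **Entry.** Section 4.1 lists "Ambulatory at baseline" as an inclusion criterion. It does not define the term or say whether baseline means before the injury or on admission.

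**Outcome.** Section 7.1 lists "inability to walk ≥ 10 feet without human assistance" among the functional outcomes.

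**Analysis.** Section 7.2 examines secondary outcomes last, "including change in OTMT, conversion to dementia, and inability to walk 10-feet". The first two are worded as changes and the third as a state. The regression models adjust for surgery type and age.

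**Assessment times.** Section 5.2.5 lists ambulation at days 60, 180 and 365. The baseline list in 5.2.3 has no ambulation entry. The schedule in 5.1 gives "Baseline Exam (Pain scales, OTMT, WHO-DAS 2.0, IADL, BRS, 3D-CAM", and the list ends there.

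**Purpose.** Section 7.2 says that the analyses taken together are to guide which outcomes a later efficacy trial uses and how it measures them.

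**The concern.** A person who walks only with another person's help can reasonably be called ambulatory, and that person already meets the walking outcome. The plan lists nothing that would identify such a patient at entry. It also has no analysis step that would separate a long-standing inability from one that arose after surgery.

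At stake is how the pilot's walking result is read. If the frequency of inability is taken as the rate of postoperative loss of walking, it will be too high. If the arms happen to differ at entry, the between-group difference will partly reflect who was enrolled rather than how blood pressure was managed. Status before surgery is easy to ask about beforehand; later it may be recoverable only by recall.

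**Working it through.** **Step 1: set the definitions side by side.**

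| Feature | Entry (4.1) | Outcome (7.1) |
|---|---|---|
| Distance | none | 10 feet |
| Human assistance | not addressed | must not be needed |
| Reference time | baseline, undefined | days 60, 180, 365 |
| Recorded as a listed item | no (5.1, 5.2.3) | yes (5.2.5) |

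The entry term is the looser of the two, so the two groups can overlap.

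**Step 2: weight of one patient.** Section 3.1 gives 25 patients at 2:1, about 17 and 8. One patient is 1/17 = 5.9 points of the intervention rate or 1/8 = 12.5 points of the control rate; two in control are 2/8 = 25 points. A patient unable at entry adds this much only if still unable at follow-up, and only if he or she would otherwise have been counted as able.

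**Step 3: illustration.** The plan states no expected frequency for the walking outcome, so there is no figure of its own to reproduce. (Its one precision figure, 16 points in 7.3, concerns delirium; it follows from 1.96 × √(0.20 × 0.80/25) = 15.7 points and does not bear on this question.) Everything below is assumed:

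- q, the share unable at entry: 5%, 10% or 20%
- risk r of new inability: 20% in control, 10% in intervention
- every patient unable at entry stays unable

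Observed risk = q + (1 − q) × r. For q = 10%, control is 0.10 + 0.90 × 0.20 = 28.0% and intervention is 0.10 + 0.90 × 0.10 = 19.0%. The share of expected control events already present at entry is q divided by the observed control risk, here 0.10/0.28 = 36%.

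| q | Expected unable at entry, of 25 | Control | Intervention | Difference, points | Risk ratio | Control events present at entry |
|---|---|---|---|---|---|---|
| 0% | 0 | 20.0% | 10.0% | 10.0 | 0.50 | 0% |
| 5% | 1.25 | 24.0% | 14.5% | 9.5 | 0.60 | 21% |
| 10% | 2.5 | 28.0% | 19.0% | 9.0 | 0.68 | 36% |
| 20% | 5 | 36.0% | 28.0% | 8.0 | 0.78 | 56% |

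The absolute difference shrinks only by the factor 1 − q. The frequency and the risk ratio move more.

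**Step 4: chance imbalance at entry.** With independent binomial counts in arms of 17 and 8, the standard deviation of the difference in the share unable at entry is √[q(1 − q)(1/17 + 1/8)]: 9.3, 12.9 and 17.1 points for q = 5%, 10% and 20%. Summing the exact binomial probabilities, the chance of a difference of 10 points or more in either direction is 31%, 47% and 60%.

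**The case against.** The strongest reply is that walking status at follow-up is a legitimate outcome. Compared between randomised arms, it gives no systematic advantage to either, because patients unable at entry are allocated by chance like everyone else. A later trial with the same entry rule would also need this status frequency for planning. All of that stands. The frequency is overstated only when it is read as new loss, and the plan does not say which reading it intends. That is a reason to report both, which a baseline item makes possible.

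Second, the forms are not shown. Eligibility Confirmation, WHODAS and the daily-living scale are all completed at baseline, and one of them might hold a usable walking question. So it would be too strong to say that these patients can never be identified. What can be said is that no listed baseline item uses the outcome's definition, although the follow-up lists name ambulation explicitly.

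Third, the consequence is small. The pilot's primary goal is feasibility and safety, walking is a secondary outcome, and the lead cognitive and functional measures in 7.2 are already changes from baseline. This also stands.

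A reader might infer that the dementia outcome has the same fault, since entry relies on "Clinical diagnosis of dementia" and "Short Blessed Test score >20" while the AD8 is not an entry criterion. The documents do not support that. Section 7.2 gives no instrument or cut-off for conversion to dementia, so there is no outcome definition for the entry rule to disagree with. The word conversion already implies a change, and the AD8 and Short Blessed Test are collected both at baseline and at day 365. What remains is a missing definition, which is a separate matter.

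A reader might also infer that the ambulatory criterion, taken literally on admission, shuts out most hip-fracture patients. The documents give no figure for this, and 4.1 and 5.2.1 expressly recruit such patients. The reference time is simply unstated.

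**Conclusion.** The point holds for walking, as a minor but worthwhile correction. Patients who need human help to walk can meet 4.1 as written, no listed baseline item identifies them, and 7.2 would count them as failures if they remain unable.

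Each such patient is worth 5.9 or 12.5 points of an arm's rate. Their number is not given. Under the assumed shares of 5% to 20%, they would make up 21% to 56% of expected control-arm events and leave a 31% to 60% chance of an entry imbalance of at least 10 points. These ranges rest on the assumed shares and on a 17:8 split; the event shares also assume a 20% control risk of new inability and no recovery of walking.

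The documents do not support a claim of systematic bias between arms. The harm is an overstated frequency of postoperative walking loss, a diluted contrast, and extra chance variation in very small arms.

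**What to change.** - **Sections 5.1 and 5.2.3:** add to the baseline assessments the same question used at follow-up, namely whether the patient can walk 10 feet without human assistance. Take it by patient or proxy report before randomisation, and state that it refers to status before the fracture or admission.
- **Section 7.2:** report new inability among patients able at baseline, by arm with a 95% confidence interval, alongside the status comparison in all randomised patients. Give the number in each arm already unable at entry. Because baseline status is fixed before allocation, the restricted comparison is still between randomised groups.

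The cost is one extra baseline question, one or two sentences in 7.2, and a slightly smaller denominator for new inability. Narrowing 4.1 to independent walkers would also remove the overlap, but it would shrink the eligible pool of a pilot that is judged partly on recruitment. It is not needed once the item is recorded.
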